5.2.7. Visit Windows

Visit windows will be used to associate assessments with a scheduled visit and will be used only for summarizing data by visit. Visit windows for safety and efficacy assessments will be defined as shown in Table 4 and Table 5. Visit windows for efficacy assessments are created ± 14 from the target day to capture the efficacy endpoints precisely.

Week	Start Day	Target Day	End Day
13	2	85	126
25	127	169	210
37	211	253	294
49	295	337	378
49+ Every 12 Weeks	$(Week-1) \times 7 - 41$	$(Week-1) \times 7 + 1$	$(\text{Week-1}) \times 7 + 42$

 Table 4.
 Visit Windows for Safety Assessments

Note: At week 41 (\pm 3 days), there will be a telephone contact to all patients to collect adverse event information only.

Note: For PRO assessments, visit windows are defined in Table 4, because the PRO schedules is the same as safety assessments.

Table 5. Visit Windows for Efficacy Assessments

Week	Start Day	Target Day	End Day
25	155	169	183
49	323	337	351
49+ Every 24 Weeks	$(Week-1) \times 7 - 13$	$(Week-1) \times 7 + 1$	$(Week-1) \times 7 + 15$

Note: the visit window is applied to the analyses by visit, such as summary tables by nominal visit, but not to the time to event endpoints analyses.

If more than 1 assessment is within a given visit window, the assessment closest to the target date will be used. If 2 assessments are equally close to the target day, the earlier assessment will be used. If there are more than 1 assessment on the same date, the assessment with the earliest collection time will be used.

At week 36 (day 246±5), there will only be PSA collection. Adjusted visit windows for PSA collection at weeks 36 and 37 will be (days 241, 246, 249) and (days 250, 253, 258) respectively.

For PRO assessments, the visit windows will be defined as shown in Table 4

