5.2.1. Visit Windows

At each specified study visit, procedures will be performed according to the schedule of activities ([Appendix 5](#)).

A study visit may be scheduled on any day within a specified study week. For any given day within the study week, the visit window is ± 5 days (ie, 5 days before or after the given day) unless otherwise stated.

Study drug supplies must be taken into account when scheduling visits during windows. Procedures for a given visit may be split across the window to allow for drug resupply and completion of study procedures.

5.2.2. Week 1, Day 1

Study site personnel will access the IWRS to assign a randomization ID number to a study participant. This number will be used to identify the patient for the remainder of the study.

Day 1 procedures are listed in [Table 2](#). Study site personnel should ensure that an approved Randomization Authorization Form is in the patient’s file before proceeding with day 1 procedures.

The blood samples for central laboratory evaluations should be collected and the patient questionnaires should be completed before the first dose of study drug to establish baseline.

If study drug cannot be administered on the same day as randomization, the patient must come to the clinic within 3 business days after randomization for the required procedures and initiation of study treatment. Day 1 is the day of randomization regardless of the date of the first dose of study drug. Note that time of first dose will be recorded in the electronic data capture (EDC) system.

Table 2. Week 1, Day 1 Procedures

Activity/Assessment	Comment
Randomization	Access the IWRS to assign randomization ID number and study drug treatment. May occur up to 3 business days before the day of first dose.
General Activities	
Vital signs and brief physical examination	May skip these assessments if performed within prior 7 days. Measure blood pressure, heart rate, temperature, and weight. Perform symptom-directed examination and investigate any new abnormalities.
ECOG performance status	Refer to Table 13 .
BPI-SF, FACT-P, EQ-5D-5L, and QLQ-PR25 questionnaires	Complete BEFORE the first dose of study drug. Refer to Appendix 1 , Appendix 2 , Appendix 3 , and Appendix 4 .
Adverse events review	Record adverse events that occurred in enrolled patients in the patient’s source documents.
Concomitant medications review	Record any new medications or changes in ongoing medications.

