The visit window is ± 5 days. Drug supply must be taken into account if a window is used to schedule the next visit.

Week 25 procedures are listed in [Table 4](#).

Table 4. Week 25 Procedures

Activity/Assessment	Comment
General Activities	
Radiographic assessments	Includes abdominopelvic CT/MRI scan and whole-body radionuclide bone scan. Chest imaging is not required. PET is not an evaluable imaging modality for this study.
Vital signs and brief physical examination	Measure blood pressure, heart rate, temperature, and weight. Perform symptom-directed examination and investigate any new abnormalities.
ECOG performance status	Refer to Table 13 .
BPI-SF, FACT-P, EQ-5D-5L, and QLQ-PR25 questionnaires	Refer to Appendix 117 , Appendix 2 , Appendix 3 , and Appendix 4 .
Symptomatic skeletal events	Record use of radiation therapy (external beam radiation therapy or radionuclides) or surgery to bone for prostate cancer, findings of clinically apparent pathologic bone fracture or of spinal cord compression, and use of opiate and/or systemic antineoplastic therapy due to bone pain.
Adverse events review	Record any new or ongoing adverse events.
Concomitant medications review	Record any new medications or changes in ongoing medications.
Study Drugs Dosing/Dispensing	As appropriate for treatment assignment.
Leuprolide injection (if applicable)	Single intramuscular or subcutaneous injection (22.5 mg).
Open-label enzalutamide dispensing (if applicable)	Provide the patient with a 12-week supply. Confirm dosing instructions with patient.
Blinded study drug dispensing (if applicable)	Provide the patient with a 12-week supply. Confirm dosing instructions with patient.
Study drug accountability	Record study drug returned and remind patient to return all study drug at each future visit.
Central Laboratory Evaluations	Refer to the central laboratory manual for sample processing.
Serum chemistry, hematology	Refer to analytes listed in Table 12 .
PSA, testosterone	

5.2.5. Week 36

The visit window is ± 5 days. The purpose of this visit is to collect a blood sample for PSA determination by the central laboratory. The course of study treatment at week 37 will be based on this test result.

5.2.6. Week 37

The visit window is ± 5 days. Drug supply must be taken into account if a window is used to schedule the next visit.

The PSA value at week 36 (central laboratory result) will determine the course of each patient's study drug treatment as follows:

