Study drug accountability	Record study drug returned and remind patient to return all study drug at each future visit (if applicable).
Central Laboratory Evaluations	Refer to the central laboratory manual for sample processing.
Serum chemistry, hematology	Refer to analytes listed in Table 12 .
PSA, testosterone	

5.2.7. Week 41

The week 41 (\pm 5 days) telephone contact will be a telephone call to all patients to collect adverse event information only.

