3.2.2. Other Secondary Endpoints

3.2.2.1. Time to distant metastasis

The time to distant metastasis is defined as the time in months from randomization to the earliest objective evidence of distant soft tissue metastases or metastatic bone disease by BICR. Soft tissue disease including lymph nodes above the aortic bifurcation and outside the pelvis and any bone metastases will be counted as distant metastases. Refer to Section 6.3.1 for details on censoring rules.

3.2.2.2. Proportion of patients who remain treatment-free 2 years after suspension of study treatment at week 37 due to undetectable PSA

The proportion of patients who remain treatment-free 2 years after suspension of study treatment at week 37 due to undetectable PSA is defined as number of patients remaining treatment-free 2 years after suspension of study treatment at week 37 due to undetectable PSA divided by the total number of patients with suspension of study drugs at week 37 due to undetectable PSA in each treatment group.

3.2.2.3. Proportion of patients per group with undetectable PSA 2 years after suspension of study treatments at week 37 due to undetectable PSA

The proportion of patients per group with undetectable PSA 2 years after suspension of study treatments at week 37 due to undetectable PSA is defined as number of patients with undetectable PSA 2 years after suspension of study treatments at week 37 due to undetectable PSA divided by the total number of patients with suspension of study drugs at week 37 due to undetectable PSA in each treatment groups.

3.2.2.4. Proportion of patients per group with undetectable PSA at 36 weeks on study drug

The proportion of patients per group with undetectable PSA at 36 weeks on study drug is defined asby the number of patients with undetectable PSA at 36 weeks divided by the total number of patients with PSA value at week 36 in each treatment group.

3.2.2.5. Time to resumption of any hormonal therapy following suspension at week 37 due to undetectable PSA

The time to resumption of any hormonal therapy following suspension at week 37 due to undetectable PSA is defined as the time in months between the date of treatment suspension at week 37 due to undetectable PSA and the date that hormonal therapy is restarted. Patients not starting hormonal therapy at the time of analysis will be censored at the date of last assessment before the analysis data cutoff date.

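### SAP 5.2.7 ends the week-36 PSA window at day 249 although week-36 draws are allowed to day 251, so the week-36 undetectable-PSA proportion may drop or replace the sample that decided suspension

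*SAP*

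**What the plan says.** **When the samples are drawn.** Protocol 5.2.5 and Appendix 5 schedule the week-36 PSA at day 246 with a window of ±5 days, and SAP 5.2.7 repeats this: "At week 36 (day 246±5), there will only be PSA collection". Of the week-36 sample, Protocol 5.2.5 says: "The course of study treatment at week 37 will be based on this test result". Protocol 5.2.6 and Appendix 5 place week 37 at day 253, also ±5. PSA is drawn again at that visit (Table 5, central laboratory row "PSA, testosterone").

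**How the SAP assigns samples to visits.** The sentence after the day 246±5 statement reads: "Adjusted visit windows for PSA collection at weeks 36 and 37 will be (days 241, 246, 249) and (days 250, 253, 258) respectively". Where two samples share a window, "If more than 1 assessment is within a given visit window, the assessment closest to the target date will be used"; ties go to the earlier sample. SAP 5.2.7 limits the windows to by-visit summaries and takes time-to-event analyses out of their scope.

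**The endpoint.** SAP 3.2.2.4 defines the proportion as the number of men with undetectable PSA at 36 weeks "divided by the total number of patients with PSA value at week 36 in each treatment group". SAP 6.3.4 analyses it with a stratified Cochran-Mantel-Haenszel test, and SAP 6.3 treats the p-value as descriptive.

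**The concern.** Two adjacent sentences of SAP 5.2.7 give different last days for week 36: day 251 for collection and day 249 for analysis. The week-36 and week-37 collection ranges overlap, and PSA is drawn at both visits, so a date alone cannot tell which visit a sample belongs to.

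The week-36 sample is also the treatment-decision sample. If the endpoint is built from dates, a man suspended for undetectable week-36 PSA could have no week-36 value in the table, or be classified by a sample that played no part in the decision. He would still count among suspended men in the two 2-year proportions. A reader of the study report could not reconcile those tables.

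**Working it through.** **Inputs.** Collection ranges are from Protocol 5.2.5, 5.2.6 and Appendix 5; analysis windows, the closest-to-target rule and the tie rule are from SAP 5.2.7.

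**Step 1: reproduce the SAP's days.** The Table 4 target formula (Week−1)×7+1 gives 35×7+1 = 246 and 36×7+1 = 253, as stated. The outer limits also agree: 246−5 = 241 and 253+5 = 258. The inner cut does not follow from ±5, since 246+5 = 251 and 253−5 = 248. It does follow from splitting the overlap at the midpoint of the two targets: (246+253)/2 = 249.5, hence 249 | 250.

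**Step 2: compare the ranges.**

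| Visit | Allowed collection days | SAP analysis window | Allowed days assigned to the other visit |
|---|---|---|---|
| Week 36 | 241–251 | 241–249 | 250, 251 (2 of 11) |
| Week 37 | 248–258 | 250–258 | 248, 249 (2 of 11) |

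**Step 3: apply the selection rule.** Take every pair with the week-36 draw on days 241–251 and a later week-37 draw on days 248–258. Week-36 days 241–247 each allow 11 later days (77 pairs); days 248, 249, 250 and 251 allow 10, 9, 8 and 7. The total is 77+10+9+8+7 = 111.

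- **No week-36 value:** draws on day 250 or 251, 8+7 = 15 pairs.
- **Week-36 sample replaced:** this needs the week-37 draw to be on day 248 or 249 (2 or 3 days from target) and the week-36 draw to be further from 246. The pairs are 241/248, 241/249, 242/248, 242/249 and 243/248, which makes 5. The pair 243/249 is a tie at 3 days and keeps the earlier sample.
- **Week-36 sample kept:** 111−15−5 = 91.

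Among the 49 pairs that are 5 to 9 days apart, 7 have no week-36 value and 5 are replaced.

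A regular 7-day gap is not immune. Pairs 241/248 and 242/249 are replaced, while 250/257 and 251/258 have no week-36 value. In the last two the deciding sample becomes the week-37 value, being 3 rather than 4 days, and 2 rather than 5 days, from day 253.

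**Step 4: test remedies.** Widening the week-36 window to 241–251 on dates alone removes the 15 empty pairs but leaves 6 replaced (the five above plus 241/250). Using the sample from the nominal week-36 visit gives 0 dropped and 0 replaced.

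These are counts of possible day pairs, not of patients.

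**The case against.** **The link to the endpoint is inferred.** SAP 3.2.2.4 and 6.3.4 refer to week 36 without citing 5.2.7, and the windows are said to serve by-visit summaries. If programming used the nominal visit label, nothing is lost. This stands as a limit on what can be claimed. Against it, only time-to-event analyses are excluded from the windows, Tables 4 and 5 have no week-36 row, and a dedicated week-36 PSA window has no evident use other than this proportion. No sentence in the SAP says that the nominal visit governs.

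**The cut is a deliberate convention.** This also stands. With collection ranges overlapping on days 248 to 251, any non-overlapping date split must misplace some allowed days. That is a reason not to rely on dates here.

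**Size.** A reader might apply 2/11 to the 1068 enrolled men. The documents do not support this: it treats a draw 4 or 5 days late as being as common as one on target, and no visit-day distribution is given. A reader might also take Protocol 5.2.1 ("A study visit may be scheduled on any day within a specified study week") to put days 246 to 252 in week 36, so that 3 of 7 days are lost. Appendix 5 and SAP 5.2.7 tie week 36 to day 246±5, and that is the basis used here.

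**Effect on the result.** A replacement changes a man's classification only if PSA crosses 0.2 ng/mL between draws that, in the five pairs, are 5 to 8 days apart. A dropped man leaves both numerator and denominator. Nothing in the documents suggests that late draws differ by arm, so no bias in the treatment comparison is shown.

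**Timing.** The Protocol synopsis has this endpoint reported with the primary MFS analysis, and Protocol 3.1 says that analysis is complete and the study unblinded. SAP 5.1.2 does not list the endpoint among the updates at the final OS analysis. This stands too: any change now is a correction after unblinding and must be labelled as such.

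**Conclusion.** The inconsistency in SAP 5.2.7 is real, and the day arithmetic is certain. Its effect on the endpoint is conditional: it arises only if the day windows were used for the week-36 proportion, which the text implies but does not say outright. Only week-36 draws 3 to 5 days early or 4 to 5 days late can be affected. The number of men cannot be computed from the documents.

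One further assumption is that study day counts from the same origin throughout. SAP 5.2.5 allows treatment start or randomization, and the edge days shift if these differ.

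A reader might infer that the suspension decision or the 2-year endpoints are compromised. They are not. Suspension follows the week-36 central-laboratory result itself, and the 2-year denominators count men actually suspended. MFS, OS and the other time-to-event endpoints are outside the windows. With a descriptive endpoint and effects confined to edge days, this is a minor point.

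**What to change.** In SAP 5.2.7, state that for 3.2.2.4 and 6.3.4:

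- the week-36 PSA is the central-laboratory sample from the nominal week-36 visit, meaning the result used for the week-37 suspension decision;
- the day window applies only when no nominal week-36 sample exists;
- a nominal week-37 sample never replaces an existing week-36 sample.

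Then confirm which derivation produced the reported week-36 table. If it was the nominal visit, only the clarifying text is needed. If it was the day windows, rerun that one table and report it as a documented post-unblinding correction, giving the number of men whose value was dropped or replaced. The cost is a short SAP clarification, a check of one derivation and, at most, one rerun table.

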5.2.8. Unscheduled Assessments

Unless otherwise specified, unscheduled assessments will not be displayed in summary tables by nominal visit/timepoint. Unscheduled assessments will be used when deriving baseline and worst case on-treatment for safety and PRO analyses. Additionally, unscheduled assessments will be used for efficacy analyses (eg, defining date of progression/censoring, date of last contact).

5.2.9. Analyses for Continuous Data

Descriptive statistics, including the number of observations (N), mean, standard deviation, median, minimum, and maximum values, will be provided for continuous variables.

In case the analysis refers only to certain visits, percentages will be based on the number of patients with a non-missing assessment at that visit, unless otherwise specified.

5.2.10. Analyses for Longitudinal Data

A mixed-model repeated measures (MMRM) approach will be used to analyze continuous data collected over time, mainly PRO data. Further details on methodology is available in a supplemental SAP specific to PRO data.

5.2.11. Analyses for Categorical Data

The number and percentage of patients in each category will be provided for categorical variables. Unless otherwise specified, the calculation of proportions will include the missing category. Therefore counts of missing observations will be included in the denominator and presented as a separate category.

In case the analysis refers only to certain visits, percentages will be based on the number of patients with an assessment at that visit, unless otherwise specified.

Some analyses will report the odds ratio and its 95% Confidence Interval (CI). The CI will first be constructed on the log-scale using the approximate variance of log (odds ratio) as (1/a) + (1/b) + (1/c) + (1/d) where a, b, c, d are the cells from a 2-by-2 table. Afterwards the log (odds ratio) and its CI will be exponentiated back to original scale.

5.2.12. Analyses for Time-to-Event Data

A 2-sided stratified log-rank test will be used for comparing treatments unless otherwise specified. Hazard ratios and the associated 95% 2-sided confidence intervals are estimated by stratified Cox proportional hazards models, including treatment as a covariate. Stratified analyses will utilize strata as defined in the randomization system unless otherwise specified. Unstratified analyses may be used in sensitivity analyses, subgroup analyses and supportive analyses, if applicable.

TTE endpoints will be summarized using the Kaplan-Meier method and estimated survival curves will be displayed graphically when appropriate. Graphs will describe the number of patients at risk over time. The median, quartiles, and probabilities of an event at particular points in time will be estimated by the Kaplan-Meier method. Confidence intervals for

medians and quartiles are based on the Brookmeyer-Crowley method. Confidence intervals for the estimated probability of event at a particular time point will be generated using the Greenwood's formula.

5.3. Methods to Manage Missing Data

Unless otherwise specified, all data will be evaluated as observed, and no imputation method for missing values will be used.

In all patient data listings, imputed values will be presented and flagged.

Missing statistics, eg, when they cannot be calculated, should be presented as 'ND' or 'NA'. For example, if N=1, the measure of variability (SD) cannot be computed and should be presented as 'ND' or 'NA'.

5.3.1. Missing Dates

For purposes of data listings, dates will reflect only the information provided by the investigator on the CRF.

If start dates for adverse events or concomitant medications are completely missing, a worst case approach will be taken whereby the events will be considered treatment emergent and the medications will be considered concomitant. If only partial information are available (eg, only a month and year or only a year) and the partial information provide sufficient information to indicate the dates are prior to the start of study treatment (eg, month/year less than month/year of first dose) then these will be considered to have started prior to treatment; if the partial information show information to indicate the date might be equal to the start of study treatment (eg, month and/or year equal to month and/or year of first dose) then the start of study treatment (eg, month and/or year equal to month and/or year of first dose) then the start of study treatment will be imputed; otherwise a similar worst case approach will apply and these will be considered to have started to have start of study treatment will be imputed; otherwise a similar worst case approach will apply and these will be considered to have started after treatment.

For the start dates for adverse events for reinitiation period, the similar approach as above will apply except the reinitiation of study treatment will be used instead of the start of study treatment.

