8.1.4. Time Period for Collecting AE/SAE Information

The time period for actively eliciting and collecting AEs and SAEs (“active collection period”) for each subject begins from the time the subject provides informed consent, which is obtained before the subject’s participation in the study (ie, before undergoing any study-related procedure and/or receiving investigational product), through and including a minimum of 30 days after the last administration of the investigational product.

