5.3.1.3. Date of Start of New Antineoplastic Therapy

Incomplete dates for new antineoplastic therapy will be imputed as follows and will be used to determine censoring dates for efficacy analyses:

- The end date of new antineoplastic therapy will be included in the imputations for start date of new antineoplastic therapy. If the end date of new antineoplastic therapy is
 - completely missing then it will be ignored in the imputations below
 - partially missing with only year (YYYY) available then the imputations below will consider 31DECYYYY as the end date of the new antineoplastic therapy
 - partially missing with only month and year available then the imputations below will consider the last day of the month for MMMYYYY as the end date of the new antineoplastic therapy

For patients who have not discontinued study treatment at the analysis cut-off date, last dose of study treatment is set to the analysis cut-off date in the imputations below.

If the start date of new antineoplastic therapy is completely or partially missing then the imputed start date of new antineoplastic therapy is derived as follows:

• Start date of new antineoplastic therapy is completely missing

- Imputed start date = min [max(PD date + 1, last dose of study treatment + 1), end date of new antineoplastic therapy]
- Only year (YYYY) for start of antineoplastic therapy is available

IF YYYY < Year of min [max(PD date + 1, last dose of study treatment + 1), end date of new antineoplastic therapy] THEN imputed start date = 31DECYYYY;

ELSE IF YYYY = Year of min [max(PD date + 1, last dose of study treatment + 1), end date of new antineoplastic therapy]

THEN imputed start date = min [max(PD date + 1, last dose of study treatment + 1), end date of new antineoplastic therapy]

ELSE IF YYYY > Year of min [max(PD date + 1, last dose of study treatment + 1), end date of new antineoplastic therapy]

THEN imputed start date = 01JANYYYY

• Both Year (YYYY) and Month (MMM) for start of antineoplastic therapy are available

IF

YYYY = Year of min [max(PD date + 1, last dose of study treatment + 1), end date of new antineoplastic therapy], AND

MMM < Month of min [max(PD date + 1 day, last dose of study treatment + 1 day), end date of new antineoplastic therapy]

THEN

imputed start date = DAY (Last day of MMM) MMM YYYY;

ELSE IF

YYYY = Year of min [max(PD date + 1, last dose of study treatment + 1), end date of new antineoplastic therapy], AND

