MMM = Month of min [max(PD date + 1 day, last dose of study treatment + 1 day), end date of new antineoplastic therapy]

THEN

imputed start date = min [max(PD date + 1 day, last dose of study treatment + 1 day), end date of new antineoplastic therapy]);

ELSE IF

YYYY = Year of min [max(PD date + 1, last dose of study treatment + 1), end date of new antineoplastic therapy], AND

MMM > Month of min [max(PD date + 1 day, last dose of study treatment + 1 day), end date of new antineoplastic therapy]

THEN

imputed start date = 01 MMM YYYY;

ELSE IF

YYYY < Year of min [max(PD date + 1, last dose of study treatment + 1), end date of new antineoplastic therapy]

THEN

imputed start date = DAY (Last day of MMM) MMM YYYY;

ELSE IF

YYYY > Year of min [max(PD date + 1, last dose of study treatment + 1), end date of new antineoplastic therapy]

THEN

imputed start date = 01 MMM YYYY.

5.3.1.4. AE Stop Date:

Ongoing events will have the AE Stop Date set to one of the following values:

- If the day or month is missing, AE Stop Date will be imputed the same way as that in Section 5.3.1.5.
- Date of Death, if imputed date is after date of death.
- If the date is completely missing, no imputation will be performed.

Adverse Events are deemed similar if they have the same verbatim term.

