6.7.5. Concomitant Medications

Concomitant medications taken during the study treatment period will be summarized for all patients in the safety population by treatment group. Medications are considered concomitant if exposure occurs during the on-treatment period. Medications will be summarized by WHO drug dictionary anatomical therapeutic chemical (ATC) classification system and generic medication name.

In addition, subsequent antineoplastic therapies will be summarized separately by treatment group. Medications will be summarized by WHO drug dictionary ATC classification system and generic medication name.

All medications recorded on the case report form will be listed.

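### SAP 5.3.1 ignores recorded stop dates when start dates are missing or partial, so events and medications that ended before first dose, and events that ended before restart, can be counted in the later period

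*SAP*

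**What the plan says.** SAP 5.3.1 covers adverse events and medications whose start date is missing or partial.

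- **Start completely missing:** "a worst case approach will be taken whereby the events will be considered treatment emergent and the medications will be considered concomitant".
- **Partial start clearly earlier than first dose:** "then these will be considered to have started prior to treatment".
- **Partial start that could coincide with first dose:** the start of study treatment is imputed. The SAP's example is "month and/or year equal to month and/or year of first dose".
- **Any other partial start:** taken as after the start of treatment.
- **Reinitiation period:** "the similar approach as above will apply except the reinitiation of study treatment will be used instead of the start of study treatment".

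None of these sentences mentions the stop date. Section 5.3.1.4 deals with adverse-event stop dates but only completes a partial one or replaces it: "Date of Death, if imputed date is after date of death". Section 5.3.1.5 covers other dates and adds no check that a start precedes its stop.

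Section 5.3.1.3, on new antineoplastic therapy, does use the other end of the interval: "The end date of new antineoplastic therapy will be included in the imputations for start date of new antineoplastic therapy".

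SAP 3.5 defines TEAEs by onset in the on-treatment period, and rTEAEs as first occurring in the dosing period after restart. On medications, SAP 6.7.5 says: "Medications are considered concomitant if exposure occurs during the on-treatment period".

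**The concern.** A worst-case convention is reasonable when the timing of an event is unknown. A recorded stop date before first dose settles the timing: the event cannot have begun on treatment. The rule overrides that information.

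Such records can exist. Under Protocol 8.1.4, adverse-event collection "begins from the time the subject provides informed consent", so an event may start and resolve before dosing. Collection continues through the suspension, so an event may resolve before restart. Protocol Table 1 asks sites to record medications stopped within 28 days before the screening visit, so medications that ended before first dose are collected by design.

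At stake is safety classification. A false TEAE dated to first dose falls in the 0-30 day category of SAP Table 10, enters the time-adjusted rates of 6.8.1 and, if grade 3 or higher, enters the time-to-first-event display. A serious event before treatment that was related to a study procedure belongs in the separate tabulation of Protocol 10.5. A false rTEAE enters tables meant to show what happens after re-treatment, where serious events may be few.

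**Working it through.** The plan gives no figure that depends on this rule, so there is nothing to reproduce. The check applies the text of 5.3.1 to nine illustrative records, each with a recorded stop before its anchor date. The anchors are assumptions: first dose 20 Jun 2018 and restart 15 Sep 2020.

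| Anchor | Recorded start | Recorded stop | Result under 5.3.1 | Imputed onset |
|---|---|---|---|---|
| First dose | missing | 10 Jun 2018 | TEAE | none assigned |
| First dose | Jun 2018 | 10 Jun 2018 | TEAE | 20 Jun 2018, 10 days after stop |
| First dose | 2018 | 10 Jun 2018 | TEAE | 20 Jun 2018, 10 days after stop |
| First dose | May 2018 | 10 Jun 2018 | prior (correct) | none |
| Restart | missing | 1 Mar 2020 | rTEAE | none assigned |
| Restart | 2020 | 1 Mar 2020 | rTEAE | 15 Sep 2020, 198 days after stop |
| Restart | Sep 2020 | 5 Sep 2020 | rTEAE | 15 Sep 2020, 10 days after stop |
| Restart | missing | 10 Aug 2018 | rTEAE | none assigned |
| Restart | Aug 2020 | 5 Sep 2020 | prior (correct) | none |

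The 198 days are 30 (rest of March) + 30 + 31 + 30 + 31 + 31 (April to August) + 15 (September).

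The rule misclassifies 7 of the 9. In 4 of these the imputed onset falls after the stop; in 3 no onset date is assigned and only the classification is wrong. The 2 partial starts in an earlier month than the anchor are handled correctly. With a check that a stop before the anchor means the event is prior, all 9 are classed as prior. The records were chosen to exercise each branch, so 7 of 9 is not an estimate of how often this happens.

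**Events between first dose and restart.** The on-treatment period in SAP 3.5 spans the suspension. An event that began after first dose and resolved before restart may therefore be a valid TEAE. The error there is its appearance as an rTEAE.

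**Medications.** With a missing start and a recorded stop before first dose, 5.3.1 returns concomitant. Section 6.7.5 requires exposure in the on-treatment period, and the stop date shows there was none.

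**Size per record.** One false event adds at most one patient to a preferred-term count, which is 100/N percentage points for denominator N. With N = 350 (planned patients per group; SAP 5.2.6 bases safety percentages on the analysis population in each group), 100/350 = 0.29. With N = 100 restarting patients in an arm, an assumption, 100/100 = 1.0. The SAP does not say which denominator the rTEAE tables use.

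**The case against.** The strongest reply has four parts.

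1. **The wording leaves room for judgement.** The month and year comparison is only an example, and imputation applies where the onset might equal first dose. A sensible programmer would see that an event resolved on 10 June cannot have started on 20 June. But the example is the only operational instruction given. It triggers on a month or year match and never refers to the stop date.

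2. **The reinitiation sentence may cover only events already belonging to that period.** It speaks of a similar approach, and the rTEAE definition requires first occurrence after restart. That reading is possible but does not remove the problem: once the restart date is imputed as the onset, the event satisfies the definition.

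3. **Section 6.7.5 is a definition and 5.3.1 a missing-data convention serving it.** This is fair, and the two are not rival definitions. Still, for a medication with a recorded early stop, the convention returns an answer that the definition excludes.

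4. **Such records should be rare.** A site must know when an event ended but not when it began, and serious events are reported within 24 hours and followed up. This stands, and it is why the point is minor.

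Three stronger readings are tempting and unsupported. A reader might infer that every affected event receives an impossible onset date; that happens only in the partial-date branch. A reader might infer a bias between arms because only patients who restart can gain false rTEAEs. But patients who do not restart can have no rTEAEs, true or false, and nothing in the documents shows that missing onset dates differ by arm. A reader might also infer damage from negative event durations, but SAP 6.8.1 plans no duration summary.

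**Conclusion.** Wrong as written, minor. Followed literally, SAP 5.3.1 counts some adverse events as treatment-emergent or as rTEAEs, and some medications as concomitant, although their recorded stop dates rule this out. It is confined to records with a completely missing start, or a partial start matching the month and/or year of the anchor, together with a stop before that anchor.

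The documents give no count of such records, so the effect on any rate cannot be calculated; it is probably small. Each false event is worth 0.29 points on 350 patients, or 1.0 point on an assumed 100 restarting patients. The conclusion rests on a literal reading of the month and year example and of the reinitiation sentence. No efficacy analysis depends on it: metastasis-free survival, overall survival and the alpha allocation are untouched.

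**What to change.** Add to SAP 5.3.1:

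- If the stop date, or the latest date compatible with a partial stop date, is before first dose, the event is not treatment-emergent and the medication is not concomitant.
- If it is before the restart date, the event is not an rTEAE.
- No imputed start may be later than the stop date, in line with the end-date bound in 5.3.1.3.
- The worst-case rule continues to apply wherever the stop date does not rule it out.

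The cost is a short SAP clarification and one condition in the date-imputation program. No new data are needed: the SAP already works with stop dates, and 5.3.1.4 and 5.3.1.5 already complete a partial stop to the last day of its month or year. SAP 6.8 still plans safety summaries after protocol amendment 5, so the change can be applied to those.
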